## 9.1.6 Post-Operative Physiotherapy Guidelines

Participants in each cohort (i.e. REGENETEN and standard surgical repair) will be provided with cohort-specific Physiotherapy Guidelines. Participants will be required to adhere strictly to the Physiotherapy Guidelines. Study personnel will remind participants of the importance of compliance, and the completion of physiotherapy sessions will be documented in the participant diary. Refer to the cohort-specific Physiotherapy Guidelines for details.

## 9.1.7 Concomitant Medications

Use of opioids, non-opioid prescription medications, and steroid injections to treat the index shoulder over 12 months following the index surgery will be documented in the participant diary or recorded from the participant's medical record per sections 9.1.4 and 9.1.5. Concomitant medications associated with the treatment of SAEs or ADEs will also be recorded.

#### 9.1.8 MRI Submissions

Upper extremity MRIs for study participants will be collected pre-operatively, at 12 months postsurgery and at 24 months post-surgery. The pre-operative MRI is the participant's standard of care MRI and will not follow the study MRI Image Acquisition Protocol. The pre-op MRI must occur within 6 months of enrollment into this study.

Participants will receive an MRI of the index shoulder at 12 months and 24 months post-surgery per the Image Acquisition Protocol. The standard of care pre-operative MRI and the 12 and 24 month MRIs will be submitted to the imaging vendor per the Image Transfer Protocol. 3T MRIs are strongly preferred for submission, wherever available, but are not required.

#### 9.1.9 Discontinued Participants

Discontinued participants are those who voluntarily discontinue participation or who are lost to follow-up after all reasonable attempts to contact them. Where possible, a final follow-up visit should be completed for all participants who discontinue the study early. Where consent is withdrawn, the date and any reason given for discontinuation should be captured, at a minimum

This document contains information that is confidential and proprietary to Smith & Nephew PLC and Smith & Nephew, Inc. and is intended for use only by Smith & Nephew and its manufacturer. It shall not be reproduced or copied in whole or in part, nor shall the contents be disclosed by any means without prior written permission from Smith & Nephew, nor shall anyone make any use of it that is contrary to the expressed or implied wishes of Smith & Nephew.

Study Protocol—Device	* smith&nephew
lieu of standard arthroscopic repair of high-grade (>50%)	Number:           REGEN.PUB.2018.09           Version: 3.0, 10SEP2019           Page: Page 31 of 105

(Section 7.7). Finally, if appropriate, the Investigator will also advise the participant of subsequent therapy and/or procedures necessary for their medical condition.

## 9.1.10 Pregnancy

Women of child-bearing potential are not excluded from the study. Pregnancy is not reportable as an adverse event; however, complications related to the pregnancy may be reportable as determined on a case-by-case basis.

## 9.2 STUDY ENDPOINTS

## 9.2.1 Performance Endpoints

*American Shoulder and Elbow Surgeons (ASES):* The ASES instrument is composed of 2 sections containing participant self-reported and clinician assessments. The ASES score is a 0 to 100-point rating based solely on participant responses and is a combination of the participant's shoulder pain rating (VAS Pain) and self-reported ability to perform 10 different activities of daily living (ADLs). ASES scores will be recorded pre-operatively, weekly from 1 week to 3 months post-surgery, and at 6,12,18 and 24 months post-surgery.

*Single Assessment Numeric Evaluation (SANE):* The SANE is a simple, single-question, patientbased shoulder function assessment tool: "How would you rate your shoulder today as a percentage of normal (0% to 100% scale with 100% being normal)?" It is popular because of its simplicity and ability to be applied to a wide variety of clinical situations. It has not been validated and no minimal clinically important difference has been reported. SANE scores will be recorded pre-operatively, weekly from 1 week to 3 months post-surgery, and at 6,12,18 and 24 months post-surgery.

Participant-reported Shoulder Pain: Pain in the participant's index shoulder will be assessed using the VAS Pain rating from the ASES instrument. The VAS Pain rating will be recorded pre-

This document contains information that is confidential and proprietary to Smith & Nephew PLC and Smith & Nephew, Inc. and is intended for use only by Smith & Nephew and its manufacturer. It shall not be reproduced or copied in whole or in part, nor shall the contents be disclosed by any means without prior written permission from Smith & Nephew, nor shall anyone make any use of it that is contrary to the expressed or implied wishes of Smith & Nephew.

Study Protocol—Device	% smith&nephew
Urocooctivo militi contor ctilav comparing UE(=ENELEN in	Number:           REGEN.PUB.2018.09           Version: 3.0, 10SEP2019           Page: Page 32 of 105

operatively, weekly from 1 week to 3 months post-surgery, and at 6, 12, 18, and 24 months postsurgery.

*Constant-Murley Score:* The Constant-Murley Score is a validated assessment of pain and shoulder functionality. The test is divided into four subscales: pain, activities of daily living, strength and range of motion (forward elevation, external rotation, abduction and internal rotation of the shoulder. At the end of the assessment, a score is obtained out of 100 points where higher scores indicate a higher quality of shoulder function. The score is obtained through a combination of participant-reported and objective (examiner-assessed) shoulder outcome measures.

*Duration of Shoulder Immobilization:* The duration of medically required shoulder immobilization following index surgery will be calculated based on the number of days in a sling, as reported in the participant diary.

*Cumulative opioid use:* Cumulative opioid use to treat the index shoulder from index surgery to 12 months will be calculated based on usage reported in the participant diary (name, dose, duration).

*Cumulative Non-opioid Prescription Medication Use:* Cumulative non-opioid prescription medication use to treat the index shoulder from index surgery to 12 months will be calculated based on usage reported in the participant diary (name, dose, duration).

*Time to Return to Work, Driving, and Sports:* Time from index surgery to return to ADLs will be calculated based on the date that participants report return to work (sedentary; laborer), return to driving, and return to sport as reported in the participant diary.

This document contains information that is confidential and proprietary to Smith & Nephew PLC and Smith & Nephew, Inc. and is intended for use only by Smith & Nephew and its manufacturer. It shall not be reproduced or copied in whole or in part, nor shall the contents be disclosed by any means without prior written permission from Smith & Nephew, nor shall anyone make any use of it that is contrary to the expressed or implied wishes of Smith & Nephew.

Study Protocol—Device	* smith&nephew
	Number:           REGEN.PUB.2018.09           Version: 3.0, 10SEP2019           Page: Page 33 of 105

*Incidence of Progression to Full Thickness Tear*. An independent reviewer will assess MRIs for evidence of progression to a full-thickness tear within 12 months and 24 months of the index surgery. All MRI assessments are detailed in the Image Review Charter.

*Percent Filling of Rotator Cuff:* An independent reviewer will assess MRIs for the percent filling of the rotator cuff at 12 months and 24 months post-surgery. All MRI assessments are detailed in the Image Review Charter.

*Rotator Cuff Tendon Thickness:* An independent reviewer will assess MRIs for the rotator cuff tendon thickness at 12 and 24 months. All MRI assessments are detailed in the Image Review Charter.

*Goutallier Classification:* The Goutallier classification will be used to classify the fatty infiltration of the rotator cuff. The Goutallier classification ranges from a grade of 0 indicating a completely normal muscles without any fatty streaks to a grade of 4 which indicates that more fat than muscle is present. An independent reviewer will assess MRIs for the fatty infiltration of the rotator cuff at 12 and 24 months post-surgery. All MRI assessments are detailed in the Image Review Charter.

*Sugaya Score:* The Sugaya score will be used to measure the rotator cuff integrity. The Sugaya score ranges from Type I to Type V. Type I indicates a repaired cuff that had sufficient thickness with homogeneously low intensity on the MRI image while Type V indicates the presence of a major discontinuity on the MRI images suggesting a medium or large tear. An independent reviewer will use the MRI to assess rotator cuff integrity at 12 and 24 months post-surgery. All MRI assessments are detailed in the Image Review Charter.

*Incidence of Revision Surgery:* All revision surgeries involving the index shoulder for any cause within 24 months of the index surgery will be documented.

This document contains information that is confidential and proprietary to Smith & Nephew PLC and Smith & Nephew, Inc. and is intended for use only by Smith & Nephew and its manufacturer. It shall not be reproduced or copied in whole or in part, nor shall the contents be disclosed by any means without prior written permission from Smith & Nephew, nor shall anyone make any use of it that is contrary to the expressed or implied wishes of Smith & Nephew.

Study Protocol—Device	Smith&nephew
lieu of standard arthroscopic repair of high-grade (>50%)	Number: REGEN.PUB.2018.09
	Version: 3.0, 10SEP2019 Page: Page 34 of 105

## 9.2.2 Economic Endpoints

Aggregate health care utilization costs: Related health care utilization costs over 12 months postsurgery will be calculated based on health care utilization as reported in the participant diary and/or in the participant's medical records.

*Operating Time (Index surgery):* Operating time for the index surgery, defined as the time from first incision to wound closure (measured in minutes) as recorded in the operative procedure notes, will be recorded.

*Medication Use:* Cumulative opioid and non-opioid prescription medication used to treat the index shoulder over 12 months following index surgery as reported in the participant diary and/or in the participant's medical record, will be recorded.

*Number of Steroid Injections:* The number of steroid injections administered to the index shoulder within 12 months of the index surgery as reported in the participant diary and/or in the participant's medical record, will be recorded.

*Number of Unscheduled Clinic Visits:* The number of unscheduled clinic visits (defined as a return visit to a health care provider for examination/evaluation of the index shoulder) within 12 months of the index surgery, as reported in the participant diary and/or in the participant's medical record, will be recorded.

*Number of For-Cause Imaging Procedures:* The number of for cause imaging procedures (e.g. MRI or ultrasound) performed on the index shoulder within 12 months of the index surgery, as reported in the participant diary and/or in the participant's medical record, will be recorded.

*Number of Physiotherapy Sessions:* The number of physiotherapy sessions within 12 months of the index surgery, as reported in the participant diary and/or in the participant's medical record, will be recorded.

This document contains information that is confidential and proprietary to Smith & Nephew PLC and Smith & Nephew, Inc. and is intended for use only by Smith & Nephew and its manufacturer. It shall not be reproduced or copied in whole or in part, nor shall the contents be disclosed by any means without prior written permission from Smith & Nephew, nor shall anyone make any use of it that is contrary to the expressed or implied wishes of Smith & Nephew.

Study Protocol—Device	Smith&nephew
lieu of standard arthroscopic repair of high-grade (>50%)	REGEN.PUB.2018.09
	Version: 3.0, 10SEP2019 Page: Page 35 of 105

## 10. STATISTICAL DESIGN

A Statistical Analysis Plan (SAP) will be written and finalized prior to database lock. The following is a brief description of the analyses to be described in this plan. If there are any changes from the analysis described below it will be detailed in the SAP and the Clinical Study Report (CSR). Any changes/additions to the analysis described in the SAP will also be detailed in the CSR.

#### 10.1 GENERAL

The CRO's Biostatistician will conduct the statistical analyses for this study, with the exception of the economic analysis, which will be conducted by Smith & Nephew's Global Biostatistics group. For the primary outcome, the significance tests and hypothesis testing will be two-sided, performed at the 5% significance level. Resulting p-values will be quoted and 95% two-sided confidence intervals will be generated where appropriate. Unless otherwise stated, point estimates (mean differences or odds ratios) and 95% confidence intervals will be reported descriptively for secondary outcome as an exploratory assessment. Select secondary outcomes will undergo statistical testing as outlined in section 10.4.2.

Where data summaries are specified, categorical and ordinal variables will be summarized with frequencies and percentages. Continuous variables will be summarized with the following summary statistics: number of observations, means and standard deviations, or median and interquartile ranges. All analyses will be performed using a statistical package such as SAS or SPSS.

#### **10.2** ANALYSIS POPULATIONS

Due to the non-randomized nature of the study design, study participants will be analyzed as per the treatment they received. Any safety analyses will include participants who received the investigational product (IP).

This document contains information that is confidential and proprietary to Smith & Nephew PLC and Smith & Nephew, Inc. and is intended for use only by Smith & Nephew and its manufacturer. It shall not be reproduced or copied in whole or in part, nor shall the contents be disclosed by any means without prior written permission from Smith & Nephew, nor shall anyone make any use of it that is contrary to the expressed or implied wishes of Smith & Nephew.

Study Protocol—Device	Smith&nephew
lieu of standard arthroscopic repair of high-grade (>50%)	Number: REGEN.PUB.2018.09
	Version: 3.0, 10SEP2019 Page: Page 36 of 105

#### 10.3 BASELINE DATA

Patient demographics and baseline outcome variables will be summarized by treatment group using descriptive summary measures expressed as means with standard deviations or medians with interquartile ranges for continuous variables depending on the distribution and number (percent) for categorical and ordinal variables.

## **10.4 EFFICACY ANALYSIS**

## **10.4.1 Analysis of Primary Endpoint**

Multiple linear regression will be used to compare differences in the mean ASES scores between the REGENETEN cohort and the comparison cohort at 3 months post-treatment. The significance tests and hypothesis testing will be two-sided, performed at the 5% significance level. Resulting p-values will be quoted and 95% two-sided confidence intervals will be generated where appropriate. The analysis will be adjusted for baseline ASES score and for differences in baseline characteristics between the two cohorts.

The minimal clinically important difference (MCID) will be used to determine the clinical importance of the mean difference between treatment groups for the ASES score and all other patient-reported outcomes (i.e. SANE, Constant-Murley score). The MCID defines the change in the outcome score that results in the smallest, appreciable clinical improvement. The MCID for the ASES is 11.1 points for patients undergoing rotator cuff repair. The criteria for determining the clinical importance of the mean difference will be as follows:

- If the confidence interval of the mean difference is completely above the MCID, the difference is considered "significant"
- If the confidence interval of the mean difference contains the MCID, the difference is considered "possibly clinically significant"
- If the confidence interval of the mean difference is completely below the MCID, the difference is considered "not clinically significant"

This document contains information that is confidential and proprietary to Smith & Nephew PLC and Smith & Nephew, Inc. and is intended for use only by Smith & Nephew and its manufacturer. It shall not be reproduced or copied in whole or in part, nor shall the contents be disclosed by any means without prior written permission from Smith & Nephew, nor shall anyone make any use of it that is contrary to the expressed or implied wishes of Smith & Nephew.

Study Protocol—Device	* smith&nephew
Prospective multi-center study comparing REGENETEN in lieu of standard arthroscopic repair of high-grade (>50%) partial-thickness tears	Number: REGEN.PUB.2018.09
	Version: 3.0, 10SEP2019 Page: Page 37 of 105

The assessment of clinical importance will be reported along with the confidence intervals for each outcome.

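### The clinical-importance rule in section 10.4.1 has no threshold at minus the MCID, so a large advantage of standard repair would get the same label as no difference

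*Combined protocol and SAP*

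**What the plan says.** Section 10.4.1 sets the primary analysis: "Multiple linear regression will be used to compare differences in the mean ASES scores between the REGENETEN cohort and the comparison cohort". The time point is the 3-month visit, and the model adjusts for baseline. On sidedness it says "The significance tests and hypothesis testing will be two-sided, performed at the 5% significance level".

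It then adds a second reading of the result. The MCID, 11.1 points for ASES, "will be used to determine the clinical importance of the mean difference between treatment groups for the ASES score" and for the other patient-reported outcomes, with SANE and Constant-Murley named. There are three categories. The top one, labelled *significant*, requires the whole interval to exceed the MCID. The middle one, labelled *possibly clinically significant*, is for intervals that include it. The lowest is worded "If the confidence interval of the mean difference is completely below the MCID, the difference is considered", and the label attached to it is *not clinically significant*.

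The MCID itself is defined in terms of benefit: "The MCID defines the change in the outcome score that results in the smallest, appreciable clinical improvement". The label does not stand alone: "The assessment of clinical importance will be reported along with the confidence intervals for each outcome".

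Section 10.4.2 and Table 2 carry the MCIDs to the secondary scores as an exploratory assessment: 11.1 (ASES), 29.4 (SANE), 5.5 (Constant-Murley) and 1.37 cm (VAS pain). No section gives a threshold at minus the MCID, an absolute value, or a label for an advantage of standard repair. Section 10 leaves further detail to a SAP that is to be finalized before database lock.

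**The concern.** A two-sided test allows for a result in favour of standard repair. The clinical-importance rule does not: everything short of +MCID falls into one category, from a trivial difference to a large one against REGENETEN. The label is the plan's prespecified statement of clinical importance for its primary endpoint. If the result went against the device, following the plan to the letter would produce the statement that the difference is not clinically significant beside an interval showing the opposite. Changing the label at that stage would be a post hoc decision.

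**Working it through.** **Inputs.** From section 11: difference 11.1, effect size 0.56, alpha 0.05, power 80%, 51 evaluable per arm. From section 10.4.1: 95% two-sided interval, threshold 11.1. The SD is not stated; it is implied by 11.1/0.56 = 19.82. Calculations are unadjusted. The contrast is REGENETEN minus standard.

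**The plan's own figure.** n per arm = 2 × (1.960 + 0.842)² / 0.56² = 50.1, rounded up to 51. This matches section 11, so the implied SD and the arm size are consistent.

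**Interval width.** SE = 19.82 × √(2/51) = 3.925. Half-width = t(0.975; 100 df) × SE = 1.984 × 3.925 = 7.79.

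**The rule as written.**

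| Estimate | 95% CI | Label in 10.4.1 |
|---|---|---|
| +20 | 12.2 to 27.8 | significant |
| +11.1 | 3.3 to 18.9 | possibly clinically significant |
| 0 | -7.8 to 7.8 | not clinically significant |
| -11.1 | -18.9 to -3.3 | not clinically significant |
| -20 | -27.8 to -12.2 | not clinically significant |

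The last row does not depend on the SD: an upper limit below -11.1 is always below +11.1.

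**Where a symmetric rule would differ.** The current label applies to every estimate below 11.1 - 7.79 = +3.31. With thresholds at both -11.1 and +11.1 that range splits in three:

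- below -11.1 - 7.79 = -18.89: interval wholly beyond -11.1 (cut-off -17.0 at SD 15, -20.9 at SD 25);
- from -18.89 to -11.1 + 7.79 = -3.31: interval contains -11.1 (upper end -5.2 at SD 15, -1.3 at SD 25);
- from -3.31 to +3.31: not clinically significant.

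**How often the label changes** (1,000,000 simulated trials per row, SD estimated in each):

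| True difference | Current rule: not | Symmetric: wholly beyond -11.1 / contains -11.1 / not |
|---|---|---|
| -11.1 | >99.9% | 2.5% / 95% / 2.5% |
| -15 | >99.9% | 16% / 83% / 0.2% |
| -20 | >99.9% | 61% / 39% / 0% |

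At a true difference of -11.1 the correction is thus nearly always to *possibly clinically significant*. At a true +11.1 nothing changes: 2.5% not, 95% possibly, 2.5% significant.

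**What the symmetric rule costs when the true difference is 0.** For ASES, the current rule gives *not clinically significant* in 80% of trials and *possibly*, favouring REGENETEN, in 20%. The symmetric rule gives 60% *not* and 20% *possibly* in each direction.

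For Constant-Murley no SD is given. Assuming 15 to 20, the half-width is 5.9 to 7.9, above the MCID of 5.5, so the interval is usually wider than the whole band from -5.5 to +5.5. At a true difference of 0, *not clinically significant* falls from 45% (SD 15) or 28% (SD 20) to about 1% or 0%.

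**When one interval contains both thresholds.** This needs a half-width of at least the MCID, that is SD ≥ MCID / (1.984 × √(2/51)): 14.0 for Constant-Murley and 28.3 for ASES.

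**The case against.** The best defence is that the rule asks a narrower question: does REGENETEN's benefit reach the MCID? The Synopsis states a superiority hypothesis, sections 4.2 and 5.1 aim to show REGENETEN superior, and the MCID is defined as an improvement. At -20 the answer to that question is indeed no. The label is also printed with the interval, it is exploratory for the secondary scores, and the SAP can still settle it. Nothing in the documents suggests that a true difference of -11.1 or worse is expected; planning is at a difference of 11.1.

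Much of this stands. It limits the practical exposure, and it means the simulated shares at negative true differences are conditional illustrations, not forecasts. It does not rescue the wording: the rule grades the difference between the groups, not REGENETEN's benefit, and it sits beside a two-sided test. An absolute-value reading would cure the problem, but it is not written and fits poorly with a definition in terms of improvement. The rule is cited to a guideline that I cannot see, so whether its source is directional cannot be judged.

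A reader might go further and infer that, because the order of subtraction is not written, an equal advantage of REGENETEN could be the one mislabelled. The documents do not support giving that equal weight. The superiority aim, the improvement wording and the order in which the cohorts are named all point to REGENETEN minus standard. Stating the sign is a clarification.

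**Conclusion.** The point holds and should be fixed. As written, on the natural reading, the rule gives the wrong label to any interval wholly below -11.1, and the same label to intervals that merely contain -11.1. That conclusion is logical and needs no SD. The split points (-18.89, -3.31, +3.31) rest on the implied SD of 19.82, 51 per arm and no covariate adjustment; if baseline adjustment worked with an assumed correlation of 0.5, the two negative ones would be -17.85 and -4.35.

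Only the clinical-importance label is affected. It would be wrong to infer that the primary test or its p-value is biased, that the sample size is wrong, or that an adverse result could be hidden: the interval is reported and shows the sign. Nor does section 10.4.1 name VAS pain among the scores for the rule. Section 10.4.2 gives it an MCID, so applying the three categories to it is an inference.

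**What to change.** In 10.4.1, 10.4.2 and the SAP:

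1. State that every difference is signed so that positive favours REGENETEN. If the rule is also to cover VAS pain, use standard minus REGENETEN with 1.37 cm and the same categories.
2. Replace the three categories with:
   - interval wholly beyond +MCID or wholly beyond -MCID: clinically significant, direction stated;
   - interval contains exactly one of +MCID and -MCID: possibly clinically significant, direction stated, and whether the interval includes 0;
   - interval wholly between -MCID and +MCID: not clinically significant;
   - interval contains both: inconclusive.

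This needs no new data, test or participants, and can be done before the SAP is finalized. ASES intervals wholly above +11.1, or containing +11.1 but not -11.1, keep their present meaning. The cost is the loss of *not clinically significant* labels under no true difference shown above: moderate for ASES, near total for Constant-Murley at the assumed SDs. The plan should say so openly. It reflects how little an interval of that width can exclude in either direction. Reporting whether the interval includes 0 keeps a *possibly* label from being over-read.
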